- We performed a retrospective cohort analysis (data pending publication) using our electronic medical records to rigorously analyze our experience with infants with normal airways presenting for elective surgery between January 24, 2015 and August 1, 2016. Of the 7125 cases performed on children younger than 12 months old, we included those managed with direct laryngoscopy without comorbidities presenting for elective surgery. We analyzed the final dataset of 1343 cases and found that 15.6% of cases required more than 1 attempt. We used our electronic medical record data logs to determine episodes of severe hypoxemia (spO₂ <90% for more than 1 minute) occurring around the time of intubation (from anesthesia start to anesthesia ready). We found that the number of laryngoscopy attempts was significantly associated with hypoxemic events (Univariate - Poisson: RR 1.4257 (95% CI 1.2576 - 1.6164) p <.0001 , Negative Binomial: RR 1.4421 (95% CI 1.2289 - 1.6922) p <.0001, GEE: RR 1.4421 (95% CI 1.2596 - 1.6510)) p <.0001), (Multivariate - Poisson: RR 1.3256 (95% CI 1.1363 - 1.5463) p= 0.0003, Negative Binomial: RR 1.3707 (95% CI 1.1327 - 1.6585) p= 0.0012 , GEE: RR 1.3707 (95% CI 1.1302 - 1.6623) p=0.0014)). Our analysis showed that the (371 of 1134) 32.7% of children with one attempt experienced severe hypoxemia while (101 of 210) 48.1% of those with multiple attempts experienced severe hypoxemia. These results are likely an over estimation of the true incidence of severe hypoxemia since there was no way for us to exclude low oxygen saturation readings related to tourniquets applied during intravenous access. Nevertheless, the differences between the two conditions (multiple vs. single attempt) are likely accurate since it is unlikely there was a disproportionate application of tourniquets in one group versus the other.

Taken together these preliminary data and prior studies demonstrate the significance of the problem and the feasibility and validity of our intervention to reduce complications. A prospective randomized trial is the only way to eliminate these issues.

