2.2 Secondary Objectives

- Number of attempts for successful intubation
- Frequency of failure to intubate with assigned device
- Frequency of complications such as hypoxemia related to intubation with the two study devices

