3.4 Study Population

3.4.1 Inclusion Criteria

- 1) Males or females age 0 to <12 months.
 - 2) Scheduled for non-cardiac surgery or procedure lasting longer than 30 minutes under general anesthesia where oral endotracheal intubation will be performed by an anesthesiology clinician.
 - 3) Parental/guardian permission (informed consent).
-

For clinician participants:

- 1) Anesthesia attending, anesthesia fellows, or anesthesia resident

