3.4.2 Exclusion Criteria

- 1) History of difficult intubation
- 2) History with abnormal airway
- 3) Predictive of difficult intubation upon physical examination
- 4) Parents/guardians who, in the opinion of the investigator, may be unable to understand or give informed consent

Subjects that do not meet all of the enrollment criteria may not be enrolled. Any violations of these criteria must be reported in accordance with IRB Policies and Procedures.

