5 STUDY EVALUATIONS AND MEASUREMENTS

5.1 Screening and Monitoring Evaluations and Measurements

5.1.1 Medical Records Review

- Demographics including MRN, name, and elements of dates including date of birth at el
 - Birth history including post menstrual age and congenital birth defect et al
 - Medical history and surgical history including diagnosis and any previous intubation history et al
-

- Chart review to collect clinical information up to 24-hour post intubation or upon discharge from PACU
- ASA physical status
- Airway assessment
- Surgical information including procedure date, type of surgical procedure, surgery length et al.
- Anesthesia records including vital signs, oxygen saturation, medications, and notes
- Post intubation assessment including complications associated with intubation

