6.3.2 Statistical Analysis

The study is powered for the primary outcome: successful tracheal intubation on first attempt. Assuming that a 10% increase in successful tracheal intubation (i.e., intubation on first attempt) is clinically meaningful, and that a reasonable rate for baseline success is (84%) (Based on our single center data) an overall sample size of 540 randomly assigned to VL or DL, will provide approximately 80 % power at the nominal two sided 5% level of significance. This calculation accounts for approximately 10% withdrawal, dropout, missing data and other data quality issues. We assume the success rate will be similar across sites. The statistical package SAS's module: PROC SEQDESIGN, was used for the sample size determination. The order of assignment of intubation method (VL vs. DL) for patients intubated by the same clinician will be done using blocked randomization with block sizes of 2, 4 or 6. The primary analysis will be based on intention-to-treat approach and include all the randomized subjects. Logistic regression will be used to compare first-attempt success proportion of tracheal intubation between DL and VL. To adjust for clinician-level clustering of outcome variable, we will apply generalized estimating equations (GEE) method to the logistic regression model to get the marginal odds ratio for first-attempt success comparing VL and DL. . We will include the patient characteristics: ASA status, thyromental distance and weight (less than 10kg, & more than 10kg) as covariates in the logistic regression model. Since there will be an interim analysis the p-value is considered significant if it is less than 0.029 to maintain the overall significance level of the study (Type I error rate) at 0.05^{14} Also, it may be that VL offers greater advantage for those with less experience such as residents as compared to attending physicians or fellows. To assess if there is this effect modification we will include class of clinicians with intervention (DL vs VL) as an interaction term in the logistic regression. In addition, we will analyze the number (not dichotomizing) of intubation attempts using a generalized linear model with the negative binomial distribution. Difference in complications, such as lowest oxygen saturation during tracheal, between treatment groups will be analyzed in multivariate linear models or generalized linear models as appropriate. General linear models and GEE

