approach will be used for these models to adjust for site-level and clinician-level clustering of outcome variables.

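### Infants with low resting oxygen saturation can enrol, but no baseline saturation term is named for the lowest-saturation and hypoxemia comparisons, which costs precision on a secondary outcome

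*Combined protocol and SAP*

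**What the plan says.** **Who may enrol.** Section 3.4.1 restricts the operation: "Scheduled for non-cardiac surgery or procedure lasting longer than 30 minutes under general anesthesia". The four exclusions in 3.4.2 are three airway items (the third is "Predictive of difficult intubation upon physical examination") and one on parental ability to consent. None concerns resting saturation, heart or lung disease, or oxygen dependence.

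**The outcome.** Section 2.2 lists as a secondary objective "Frequency of complications such as hypoxemia related to intubation with the two study devices", and 1.1 singles out hypoxemia as the complication that VL is expected to reduce. For the trial itself, no threshold, duration, time window or reference value is given.

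**The supporting cohort.** Section 1.3 defines severe hypoxemia as SpO2 under 90% for over a minute, between anesthesia start and anesthesia ready. On the cohort's population it says "we included those managed with direct laryngoscopy without comorbidities presenting for elective surgery".

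**The analysis.** Section 6.3.2 says "Difference in complications, such as lowest oxygen saturation during tracheal, between treatment groups will be analyzed in multivariate linear models", or generalized linear models where suitable. It lists no covariates for these models. It adds only that general linear models and a GEE "approach will be used for these models to adjust for site-level and clinician-level clustering of outcome variables". The sentence beginning "We will include the patient characteristics: ASA status, thyromental distance and weight" belongs to the logistic model for first-attempt success.

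**The data.** Section 5.1.1 lists "Anesthesia records including vital signs, oxygen saturation, medications, and notes", and 4.2.4 also lists oxygen saturation. No reading is designated as the baseline.

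**The concern.** An infant's lowest saturation around intubation is the starting value less any fall. Only the fall can reflect the device. Without the starting value in the model, differences between infants at rest stay in the residual.

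The supporting cohort kept this variation down by leaving out infants with comorbidities. The trial does not carry that restriction over. An infant with heart or lung disease, a normal airway and a non-cardiac operation is eligible and may start at a low level. If hypoxemia were judged against an absolute cut-off, such an infant could be an event under either device.

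At stake is the precision of the comparison on the complication that the hypothesis names.

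**Working it through.** **1. What the plan gives.** It states no SD, effect size or power for saturation or hypoxemia. Its only sample size is for first-attempt success: 167 per arm; 167/0.90 = 185.6, rounded up to 186; 186 × (1 + 9 × 0.05) = 186 × 1.45 = 269.7, rounded up to 270. Nothing below alters this. The 270 is used only as the number per arm.

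**2. Dilution under an absolute threshold.** Let a share q of infants be events whatever the device. The observed rate in an arm is q + (1 − q)p, where p is the rate among the other infants. For DL, p = 33% is close to the cohort's one-attempt figure (371/1134 = 32.7%). For VL, p = 25% is assumed. The share q is not in the documents; 1% to 5% is assumed, or about 5 to 27 of 540 infants.

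| q | DL | VL | Risk ratio | Difference (points) |
|---|---|---|---|---|
| 0 | 33.00% | 25.00% | 0.758 | 8.0 |
| 1% | 33.67% | 25.75% | 0.765 | 7.9 |
| 3% | 35.01% | 27.25% | 0.778 | 7.8 |
| 5% | 36.35% | 28.75% | 0.791 | 7.6 |

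The ratio moves more if hypoxemia is rarer. With assumed rates of 20% and 12%, it goes from 0.600 to 0.1288/0.2080 = 0.619 at 1% and 0.1640/0.2400 = 0.683 at 5%.

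**3. No bias between devices.** If both arms share the same p, both observed rates equal q + (1 − q)p, so the null hypothesis is preserved. A simulation with 270 independent infants per arm and a common rate of 32.7% rejected in 4.9% of runs at q = 0, 5.2% at q = 5% and 5.1% at q = 10%, against a nominal 5%.

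**4. Noise in lowest SpO2.** Assume an SD of 8 points among the other infants and a lowest value d = 10 to 15 points lower in the affected share. The variance is multiplied by 1 + q(1 − q)d²/64.

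- q = 1%: 1 + 0.0099 × 100/64 = 1.015, up to 1 + 0.0099 × 225/64 = 1.035.
- q = 5%: 1 + 0.0475 × 100/64 = 1.074, up to 1 + 0.0475 × 225/64 = 1.167.

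Taking square roots, the standard error rises by about 1% to 8%.

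**5. Chance imbalance.** Take five affected infants split 4 to 1, each 12.5 points lower. The mean difference shifts by 3 × 12.5/270 = 0.14 points. The standard error, ignoring clustering, is 8 × √(2/270) = 0.69 points. The shift is about 0.2 standard errors.

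**6. Gain from the covariate.** If baseline and lowest SpO2 correlate at r, adjustment leaves 1 − r² of the variance: 91% at r = 0.3, 75% at 0.5 and 51% at 0.7 (r assumed).

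**The case against.** A reader might infer that the trial counts pre-existing desaturation as an intubation complication. The documents do not support that. The rule of SpO2 under 90% for over a minute is the retrospective cohort's and is never adopted for the trial. The trial's own wording points the other way: the objective ties hypoxemia to intubation, research staff must watch the intubation and record it (4.2.3), the case report form takes events related to intubation (5.2), and time of onset and causality are recorded (8.3). A low reading present before laryngoscopy would not naturally qualify. This objection stands for reported events. It does not reach lowest saturation, which is a measurement and involves no attribution.

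A reader might also infer that the plan rules out a baseline term. It does not: the covariates of these models are left open. The term is unstated, which is still a gap in pre-specification.

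Thirdly, allocation is 1:1 and stratified, so omitting the covariate leaves the comparison valid. Ordinary chance imbalance is already reflected in the confidence interval. This stands in full and limits the point to precision and dilution.

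**Conclusion.** The point holds as a modest gap in a secondary analysis. The criteria admit infants with low resting saturation, the supporting cohort left out infants with comorbidities, and no baseline saturation term is named for the complication models. There is no bias towards either device, no excess type I error, and no effect on the primary endpoint or the sample size.

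Under the main assumptions the harm from low-baseline infants is small: at 1% the risk ratio is still 0.76 to two decimals, and at 5% it is 0.79. It would be larger if hypoxemia were rarer than in the cohort. The dilution arises only if an absolute threshold is used. The more general gain is the reduction in residual variance of lowest SpO2, which does not depend on how many such infants enrol. Prevalence, the VL rate, the SD, the deficit and the correlation are all assumed, so the true size cannot be established from the documents.

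**What to change.** In 6.3.2:

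- Pre-specify the pre-induction SpO2 from the anesthesia record as a covariate in the lowest-saturation model and the hypoxemia models, alongside the clustering adjustment already planned.
- State which reading counts as pre-induction, and give a simple rule for infants without one.
- Add a sensitivity analysis that excludes infants already below whatever hypoxemia threshold the trial adopts. This requires the trial to state its threshold, which it does not now do.

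Eligibility, sample size and the primary analysis stay as they are. The cost is SAP wording plus one explicitly abstracted value per infant, since 4.2.4 and 5.1.1 list oxygen saturation only in general terms. Some readings may be missing or affected by artefact; 1.3 itself reports that tourniquets applied for intravenous access could produce low readings. An artefactual baseline weakens the precision gain but does not bias the randomized comparison, provided that the reading precedes use of the device.

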6.3.3 Efficacy Analysis

The primary analysis will be based on an intention to treat approach and will include all randomized subjects.

The primary efficacy endpoint will be a successful tracheal intubation following the procedure. We will consider a 10% improvement between VL compared to DL to be indicative of a significant clinical effect. The statistical analysis of this change will be based on a logistic regression model where an odds ratio greater than 2.98 will be considered evidence of efficacy of VL compared to DL. Marginal odds ratios with 95% confidence intervals will be reported for the sample overall, as well as each site, if appropriate.

6.5 Interim Analysis

There will be an interim analysis after 224 evaluable subjects are enrolled. The proportion of subjects that are successfully intubated at the first attempt will be compared for VL and DL using logistic regression with $\alpha = 0.029$ for significance. This more stringent criteria for significance (0.029 instead of 0.05) is Pocock's method of correction for maintaining overall study significance level at .05 when there is one interim analysis. We will include ASA status, thyromental distance and weight less than 10kg as covariates in the logistic regression. The probability of stopping at the interim analysis (mid-point) is 46.4%, if the true improvement in intubation first attempt success rate is 10.0% (i.e. 84% true first attempt success rate for DL vs. 94% true success rate for VL). However, if the true improvement in first attempt intubation success rate is 12.0% (i.e. 84% vs 96% for DL and VL respectively), then the probability of stopping early increases to 83.0%.

7 STUDY DEVICE

7.1 Description

Both Storz C-Mac Video Laryngoscope (VL) and Standard Direct Laryngoscope (DL) are FDA approved and used clinically for study population at all participating center.

Standard Direct Laryngoscope

Storz C-Mac blade

The Storz C-Mac blade is a standard direct style blade with a CMOS camera embedded at the distal tip. The image from the camera is transmitted to a foldable display on the handle of the device. The imaging display is viewable by nearby other clinicians.

The standard direct blade is a rigid style, visualization occurs by direct line of sight.

8 SAFETY MANAGEMENT

8.1 Clinical Adverse Events

Clinical adverse events (AEs) related to intubation will be monitored throughout the study.

8.2 Adverse Event Reporting

Unanticipated problems related to the research involving risks to subjects or others that occur during the course of this study (including SAEs) will be reported to the IRB in accordance with institutional IRB SOP. AEs that are not serious but that are notable and could involve risks to subjects will be summarized in narrative or other format and submitted to the IRB at the time of continuing review.

8.3 Definition of an Adverse Event

An adverse event is any untoward medical occurrence in a subject who has received an intervention (drug, biologic, or other intervention). The occurrence does not necessarily have to have a causal relationship with the treatment. An AE can therefore be any unfavorable or unintended sign (including an abnormal laboratory finding, for example), symptom, or disease temporally associated with the use of a medicinal product, whether or not considered related to the medicinal product.

All AEs related to the study intervention/intubation will be noted in the study records and on the case report form with a full description including the nature, date and time of onset, determination of non-serious versus serious, intensity (mild, moderate, severe), duration, causality, and outcome of the event.

9 STUDY ADMINISTRATION

9.1 Treatment Assignment Methods

9.1.1 Randomization

The randomization schedule will be generated by statistician and randomized by using REDCap randomization feature. To avoid protocol violation, the randomization option in REDCap is only available to consented subjects when consented and anesthesia clinicians are scheduled to perform the intubation. Randomization schedule will be maintained by study manager at DCC in REDCap. The randomization will be stratified by site and clinicians role to ensure an equal number of study DL or VL participants at each center. REDCap will keep a permanent and unchangeable randomization records.

9.1.2 Blinding

Blinding of the PI and clinician is not feasible in this study. The statisticians will be blinded at the time of generating the randomization schedule and remain blinded at the time of analysis.

9.2 Data Collection and Management

DCC will be housed at CHOP. CHOP could also be IRB of record for other US based participating sites. CHOP REDCap will be utilized as Electronic Data Capture (EDC).

Minimal identifiable information might be printed on paper for study eligibility clarification, study data collection, and data validation. Any un-needed paper data which has identifiable information could be shredded as soon as possible per institutional policy.

Study electronic records will be stored in institutional approved secured network drives or websites or databases, which are fully tracked with user credentials and only authorized research personnel have the access. Paper records will be secured in a locked office where only authorized research personnel have access.

9.3 Data Transfer

Study data including identifiers (MRN and names) and dates will be entered in the study EDC. Scanned ICF could be uploaded to study EDC for monitoring. Full dataset could be exported from the EDC and saved in the DCC secured network for study monitoring and auditing, and data management. Only the site study staff and DCC would have access to site identifiers. Coded Limited dataset (including dates) could be shared with the statistician for data analysis and participating centers.

9.4 Retention

When the study is completed, all study paper records might be scanned and then destroyed to store along with other electronic study records for retention. These will be stored and backed up in an institutional approved secured network drive, website or database. Only authorized study personnel will have access. All study materials, including PHI and the master list, though not the information linking subject PHI with study data, will be retained for 10 years after the subjects turn 18 years old. Then the master link code will be permanent deleted.

9.5 Confidentiality

All data and records generated during this study will be kept confidential in accordance with each site's Institutional policies and HIPAA on subject privacy. The Investigator and other site personnel will not use such data and records for any purpose other than conducting the study. Safeguards to maintain subject confidentiality are described under Data Collection and Management.

No identifiable data will be used for future study without first obtaining IRB approval. The investigator will obtain a data use agreement between the provider (participating centers) of the data and the recipient researchers (CHOP) before sharing a limited dataset (PHI limited to dates).

HIPAA does not apply to clinician participants.

10 REGULATORY AND ETHICAL CONSIDERATIONS

10.1 Data and Safety Monitoring Plan

The participating center's principal investigator will oversee the safety of the data and that of the research subjects. During the study period, each subject will be monitored for any adverse events or safety concerns. Contacts will be provided to all enrolled subject's parents/legal guardians with any concern. Study principal investigator will oversee overall safety of data.

10.1.1 Risk Assessment

Both devices are approved and used in accordance with their labeling, both approaches are currently used as part of routine clinical care at the institution; experienced clinicians will oversee the procedure and the protocol allows for cross-overs. The main risk of the study is due to randomization (to an intubation approach the subjects may not have undergone if their clinician had made the decision). Additionally VL may take longer however this has been shown to be clinically insignificant in all studies. The risks are no greater than minimal.

10.1.2 Potential Benefits of Trial Participation

This study might benefit some participants by faster intubation. They may have fewer intubation attempts thereby reducing intubation related risks.

Risk-Benefit Assessment

The risks of this study are no different than those associated with current practice for airway management in children undergoing general anesthesia for elective surgery. There are potential benefits to the greater population of children in that we will have knowledge about the efficacy of VL vs DL.

